### **SIGNATURES**

# 2 Summary

The aim of this NIS is to collect further knowledge on the routine use of pre-rolled TachoSil® in laparoscopic surgery, especially in the field of gynecology, urology and visceral surgery where its hemostatic and sealing properties [see Summary of Product Characteristics (SmPC)] help to reduce the rate of postoperative complications, especially of postoperative bleeding and lymph leakage.

### **Short Title of Study**

RollOut - Pre-Rolled TachoSil® in Laparoscopic Utilisation. A Non-Interventional Study

# Study sites

Up to 50 German and 10 Austrian hospitals performing laparoscopic surgery, from departments of gynecology, urology and visceral surgery. The number of centres is subject to adjustment.

### **Objectives**

- To describe ease of use and satisfaction with application of pre-rolled TachoSil® in laparoscopic procedures within approved therapeutic indication (SmPC).
- To assess whether pre-rolled TachoSil® is valuable from the surgeon's view for reducing post-surgical complications, especially bleeding and lymph leakage.
- To perform a costs analysis (length of hospital stay, avoidance of complications, cost savings etc.) based on information given by physicians and pecuniary considerations.
- To describe safety in the routine use of pre-rolled TachoSil® in laparoscopic use.

# Methodology

Observational Model: Cohort, Time Perspective: Prospective

#### **Number of patients**

A sample size estimation resulted in a total number of 465 patients (please refer to Chapter 11.3). The final number of enclosed patients is determined by the number of available patients with pre-rolled TachoSil®. It is planned to include up to 105 Austrian and 360 German patients who will have laparoscopic surgery, especially in the field of gynecology, urology and visceral surgery and pre-rolled TachoSil® is used.

## Diagnosis/Disease/Condition and main criteria for inclusion

### **Inclusion Criteria:**

Inpatients planned for laparoscopic surgery, in the field of gynecology, urology and abdominal surgery where pre-rolled TachoSil® was applied, 18 years or older.

### **Exclusion Criteria:**

- Contraindications, such as hypersensitivity to the active pharmaceutical ingredients or to other components of pre-rolled TachoSil®, according to the current SmPC.
- Patient participates in another clinical trial.

### **Duration of data collection per patient**

Observational period for individual patient: from surgery (V0: Baseline) until date of discharge from hospital (V1: Final visit).

#### Criteria for evaluation

### Population descriptors

Inpatients planned for laparoscopic surgery, in the field of gynecology, urology and visceral surgery where pre-rolled TachoSil® was applied and at least 18 years of age.

#### Main outcome variables

#### Primary

- Assessment by the surgeon with respect to ease of use and overall satisfaction in the application with pre-rolled TachoSil®, using 5-Point-Likert-Scales (1 = easy/satisfied, 5 = difficult/ not satisfied)

[Time Frame: intra- and post-surgery until hospital discharge]

#### Secondary

- Length of hospital stay (ICU and normal hospital station)
   [Time Frame: Date of surgery until hospital discharge]
- Pharmaco-economic evaluation as assessed by the surgeon
   [Time Frame: intra- and post-surgery until hospital discharge]
- Intra- and post-operative adverse events, especially including bleeding and lymph leakage

[Time Frame: from study start to study end]

## Health economics

Cost analysis (length of hospital/ICU stay, avoidance of complications, cost savings) based on information given by physicians and pecuniary considerations (cost per minute of surgery/day in ICU/day in normal ward)

#### Statistical methods

For the analysis of data the safety population (SAF) only will be considered. The safety population consists of all patients,

- who received a patient information and who had consented to the collection, transmission and evaluation of their data (Comment: this has to be documented in the CRF and it is assumed that the consent forms are available for all patients in the corresponding study center.), and
- who underwent laparoscopic surgery in the field of gynecology, urology and visceral surgery with pre-rolled TachoSil® applied during surgery as documented in the CRF.

The SAF is used for summaries of demographic and baseline characteristics, all safety related variables and all summaries of effectiveness data. No per-protocol- set analysis will be done.

All data collected will be analyzed descriptively. In general, numerical continuous or 'quasi'-continuous data will be summarized with standard descriptive statistics including number of patients with valid data, arithmetic mean, standard deviation, minimum, median and maximum. For categorical variables tables of frequencies (absolute and relative frequencies) will be presented. The percentages are based on the number of patients in column heading unless otherwise stated. The number of patients with missing values is included in the calculation of the percentages.

Statistical analyses will be performed using validated statistical software (e.g. SAS®, SAS Institute Inc.). All statistical details including calculated variables and proposed format and content of tables will be detailed in a separate document, the statistical analysis plan (SAP). The SAP will be provided by the CRO and finalized before study database lock.

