# 4 Study Objectives

- To describe ease of use and satisfaction with application of the pre-rolled TachoSil® in laparoscopic procedures within approved therapeutic indication (SmPC).
- To assess whether pre-rolled TachoSil® is a valuable tool from the surgeon's view for reducing post-surgical complications, especially bleeding and lymph leakage.
- To perform a costs analysis (length of hospital stay, avoidance of complications, cost savings etc.) based on information given by physicians and pecuniary considerations (Euro)
- To describe safety in the routine use of pre-rolled TachoSil® in laparoscopic surgery.

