# 2 Analysis

## 2.1 Sample Size

Due to the character of this study (observational, non-interventional, no randomization or control group), only descriptive analysis will be conducted and no hypothesis will be tested. It is planned to include approximately 120 patients in this non-interventional study.

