# 4 Study Variables

Continuous variables will be analysed using minimim, maximum, arithmetic mean, median.

For discrete variables (ordinal, nominal), the frequency (absolute and relative) will be reported (arithmetic mean and median optionally).

If there are free text entries, these will be coded using dictionaries, if necessary.

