## 4.2.1 Complications

- Any complications after TachoSil application
  - o Yes / No: Frequencies
- Number of Adverse Events
  - o Minimum, maximum, median, arithmetic mean

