#### 4.3 Documentation of Adverse Events

Adverse Events will be reported immediately to the Sponsor's Pharmacovigilance department.

- Pregnancy: Yes No: Frequencies
- Description of Adverse Event
  - o Coding with MedDRA
    - Grouping by SOC, PT: Frequencies
- Causality: Yes / No: Frequencies
- Severity: Frequencies
- Actions taken
  - o Frequencies
  - o Other: coding if possible
- Outcome: Frequencies
  - o If sequalae: coding of free text
  - o If death: autopsy: yes no: frequencies
- Serious: Yes / No: Frequencies
- SAE criteria: checked: Frequencies

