# 7 Analysis Details

Data analysis will be done using Statistics Software (Excel 2010, MedCalc 17.8.6).

Descriptive Statistics will be used (No testing of hypotheses):

- Number of observations
  - o Absolute
  - o Relative
- Arithmetic Mean
- Median
- Minimum
- Maximum

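### The SAP summarises safety in about 120 patients by counts and percentages alone, with no interval to show which event rates remain compatible with the data

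*Protocol*

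**What the plan says.** The protocol (section 4) sets as one of four objectives "To describe safety in the routine use of pre-rolled TachoSil® in laparoscopic surgery", and SAP section 3 repeats it. The secondary outcomes in the protocol Summary include "Intra- and post-operative adverse events, especially including bleeding and lymph leakage".

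The planned method is frequencies throughout. The protocol Summary (Statistical methods) says "For categorical variables tables of frequencies (absolute and relative frequencies) will be presented", and protocol section 11 repeats the rule. Section 11.1 adds a listing of all AEs, and listings or tables in periodic safety report style. SAP section 4 says "For discrete variables (ordinal, nominal), the frequency (absolute and relative) will be reported". SAP 4.2.1 has a yes/no item, "Any complications after TachoSil application", summarised by frequencies. SAP 4.3 gives "Grouping by SOC, PT: Frequencies" for coded events, and frequencies for causality, severity, outcome and seriousness. SAP section 7 restricts the analysis to descriptive statistics and lists absolute and relative numbers, mean, median, minimum and maximum.

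On size, SAP 2.1 states: "It is planned to include approximately 120 patients in this non-interventional study". SAP 1.6 places 120 patients in up to 12 Austrian centres. The protocol (sections 2 and 11.3) plans up to 465.

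**The concern.** A percentage from about 120 patients is imprecise when events are rare, and nothing in the planned output shows how imprecise. The protocol Introduction says that the pre-rolled form has not been studied in clinical trials. Sections 7.1 and 13 foresee posting, publication and regulatory use of the results. The event percentages are therefore likely to be read as early safety information on this form.

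Precision for safety was not considered when the study was sized. The only derivation, in protocol 11.3, concerns a handling score, and the SAP gives no derivation for about 120. Neither document says what a low or zero count would leave open.

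**Working it through.** **1. The plan's own sample size.** Inputs from protocol 11.3: null proportion 0.18, alternative 0.09, two-sided alpha 0.05, power 80% or 90%, one-group chi-square test.

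n = [z(1−α/2)·√(p0(1−p0)) + z(power)·√(p1(1−p1))]² / (p0−p1)²

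- 80%: [1.960·√0.1476 + 0.842·√0.0819]² / 0.0081 = 121.9, so 122.
- 90%: [1.960·√0.1476 + 1.282·√0.0819]² / 0.0081 = 154.8, so 155.
- Three surgical fields: 3 × 122 = 366 and 3 × 155 = 465.

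The protocol's figures reproduce. They rest on the handling score and use no safety event rate.

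**2. Exact intervals for an event proportion.** Inputs: N = 120 (SAP 1.6 and 2.1) and N = 465 (protocol 11.3). The event counts x are illustrative.

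Two-sided 95% Clopper-Pearson limits: lower = Beta quantile(0.025; x, N−x+1), upper = Beta quantile(0.975; x+1, N−x). For x = 0 the lower limit is 0 and the upper limit is 1 − 0.025^(1/N).

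| N | Events | Observed | 95% interval |
|---|---|---|---|
| 120 | 0 | 0% | 0 to 3.03% |
| 120 | 1 | 0.83% | 0.02 to 4.56% |
| 120 | 3 | 2.5% | 0.52 to 7.13% |
| 120 | 6 | 5.0% | 1.86 to 10.57% |
| 465 | 0 | 0% | 0 to 0.79% |
| 465 | 3 | 0.65% | 0.13 to 1.87% |

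For zero events, 1 − 0.025^(1/120) = 3.03% and 1 − 0.025^(1/465) = 0.79%. The ratio is 3.03 / 0.79 = 3.8. Wilson intervals at N = 120 agree within about half a percentage point (0 events: 0 to 3.10%).

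**3. Chance of seeing no event, (1−p)^N.**

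- N = 120: 30% if the true rate is 1%, 8.9% at 2%, 2.6% at 3%, 0.2% at 5%.
- N = 465: 0.9% at a true rate of 1%.

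**4. Whether a reader could derive the interval from the planned tables.** This needs the number of patients with the event and a clear denominator.

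- SAP 4.3 does not say whether its frequencies count patients or events.
- The protocol Summary includes patients with missing values in the percentages, whereas SAP 8.2 leaves missing data out.
- As outcomes, bleeding and lymph leakage appear in the SAP only in the objectives (section 3). No analysis item or set of coded terms defines them.

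**The case against.** The strongest reply is that the study is descriptive. SAP 2.1 and 7 exclude hypothesis testing, and no section plans to rule out any event rate, so the missing interval contradicts nothing. That is correct. A reader might infer that the safety objective fails without intervals, but the documents promise only description. An interval is nevertheless an estimate and not a test, so it fits such a design.

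The plan also reports counts with percentages, and the example table in SAP 7.1.1 shows n, % and a total. A reader might infer that a bare 0% would be printed with its basis hidden. The documents do not support that. What remains is that the count is not defined at patient level and the denominator rules differ, so deriving an interval from the tables would be unreliable.

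A reader might also infer that a zero count in 120 leaves rates such as 5% open, or that the observed rate is always compatible with one at least three times higher. Neither holds. Zero of 120 is incompatible with 5% (probability 0.2%). For 3 of 120 the ratio of upper limit to estimate is 7.13 / 2.5 = 2.9, and for zero events a multiple has no meaning.

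The interval displays imprecision and does not reduce it. Nor does it settle why the protocol plans 465 patients and the SAP about 120, which is a separate question: the SAP cites a protocol dated 22 February 2016, and the protocol reviewed here carries 20 August 2015.

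Finally, a binomial interval ignores clustering by centre and the selection bias admitted in protocol 7.2, including enrolment of patients whose surgical outcome is known. This stands, and calls for a note beside the table.

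**Conclusion.** The point holds as a cheap improvement to the reporting of safety, mainly in the SAP. Neither document plans any measure of precision for the safety outcomes. With 120 patients the exact 95% upper limit is 3.0% for no events, 4.6% for one and 7.1% for three. With 465 patients and no events it is 0.8%, so the practical weight of the point depends on the SAP's smaller number.

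The figures assume independent patients, each counted once, over a denominator of exactly 120 or 465. Clustering in up to 12 centres would tend to widen the intervals, but the documents give no intraclass correlation. Selection is not covered by any of these limits.

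**What to change.** - In SAP 4.2.1, 4.3 and 7, and in protocol section 11, report a two-sided 95% Clopper-Pearson interval for the proportion of patients with at least one AE, SAE, related AE, bleeding event and lymph leakage. Give the upper limit when the count is zero.
- State that patients are counted, not events, and that the denominator is every patient in the Safety Analysis Set. Reconcile the missing-value rule in the protocol Summary with SAP 8.2.
- List the MedDRA terms that define bleeding and lymph leakage.
- In SAP 2.1, and not in the objective, state that if no event of a given type is seen in 120 patients, true rates up to about 3% remain compatible with the data. The sentence must be conditional on a zero count, because the limit is higher once an event is seen.
- Beside the table, note that the intervals assume independent patients and do not cover centre clustering or the selection bias acknowledged in protocol 7.2.

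No new data are needed. The cost is one more table column, agreement on the term lists and denominator, and a safety statement that looks less favourable. SAP version 1.0 is dated September 2017 and its last patient visit is planned for September 2018, so on these dates it could be amended before database lock.

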# **APPENDICES**

1. SmPC, TachoSil® sealant matrix, German language 09/2014

### **List of Abbreviations and Definition of Terms**

AE: Adverse Event

ADR: Adverse Drug Reaction

CA: Competent Authority

CCSI: Core Company Safety Information

CRF: Case Report Form

CRO: Contract Research Organisation

CV: Curriculum Vitae

GCP: Good Clinical Practice

GPP: Good Pharmacoepidemiology Practices

ICH: International Conference on Harmonisation

ICU: Intensive care unit

IDS: International Drug Safety

IEC: Independent Ethics Committee

IRB: Institutional Review Board

NIS: Non-interventional study

PP: Per Protocol

PSUR: Periodic Safety Update Report

SAE: Serious Adverse Event

SAF: Safety Population

SAP: Statistical Analysis Plan

SADR: Serious Adverse Drug Reaction

SmPC: Summary of Product Characteristics

### 3 Introduction

TachoSil® consists of a collagen sealant matrix coated with human fibrinogen and human thrombin for use as a local haemostatic and tissue sealing. This fixed combination is applied directly to the wound surface. Upon contact with blood, body fluids, or physiological saline, the components of the coating dissolve and diffuse into the wound surface. Thrombin converts fibrinogen into fibrin, mimicking the final stage of the coagulation cascade, and forming a cross-linked fibrin clot, which holds the collagen matrix tightly to the wound surface providing local haemostasis and tissue sealing. The active side of the coating sealant matrix is marked in yellow.

Extensive experience on the use of TachoSil® in open invasive surgery and its relevant results in respect to reduction of time to hemostasis, change in length of hospital stay and decrease in postoperative complications encouraged surgeons to apply TachoSil® in minimal invasive (laparoscopic) surgery as well. As laparoscopic techniques require the application of TachoSil® through a trocar, surgeons started preparing TachoSil® themselves raising the need to develop a pre-rolled form which was approved by the European Medicines Agency's Committee for Medicinal Products for Human Use (CHMP) in September 2014.

No clinical trials using pre-rolled TachoSil have been performed. This real-world observational study is conducted to obtain an overview on the ease of use of pre-rolled TachoSil® in laparoscopic use, especially when performing gynaecological, urological and visceral surgery. Additionally, users' satisfaction with the product will be evaluated to confirm procedural advantages of the pre-rolled form in laparoscopic use.

# 4 Study Objectives

- To describe ease of use and satisfaction with application of the pre-rolled TachoSil® in laparoscopic procedures within approved therapeutic indication (SmPC).
- To assess whether pre-rolled TachoSil® is a valuable tool from the surgeon's view for reducing post-surgical complications, especially bleeding and lymph leakage.
- To perform a costs analysis (length of hospital stay, avoidance of complications, cost savings etc.) based on information given by physicians and pecuniary considerations (Euro)
- To describe safety in the routine use of pre-rolled TachoSil® in laparoscopic surgery.

# 5 Study Administrative Structure

# 5.1 Study Sites

Up to 50 German hospitals and 10 Austrian hospitals performing laparoscopic surgery, including departments of gynecology, urology and visceral surgery. Sponsor/CRO will keep a record of the individuals responsible for each participating Study Site, the Site Responsibles.

# **5.2 Sponsor Personnel**

Sponsor will keep a record of all relevant sponsor personnel. Sponsor will be in charge of relevant document submission to Regulatory Authorities and Independent Ethics Committees (IECs) / Institutional Review Boards (IRBs).

# 5.3 Contract Research Organisation (CRO)

The CRO will be in charge of document development, monitoring, data management, Statistical Management Plan, analysis and generation of a study report. Details of the tasks and responsibilities are regulated in the study task order between the sponsor and the CRO.

The CRO will keep a record of all involved CRO personnel.

#### 5.4 Essential Documents

The following essential documents must be received by Sponsor/CRO before the study is initiated at a site:

- Written agreement, including section of protocol agreement between Takeda and the Study Site Responsible/Hospital.
- Patient Information Sheet and Informed Consent Form in local language (notified to / approved by Independent Ethics Committees (IECs) as locally required
- Written IEC vote according to local regulations
- Authority notification according to local regulations

#### 6 Ethics

This study is an observational study where the existence of the study has no impact on the patient except for collection of informed consent to use of the patient's data.

# 6.1 Ethical conduct of the Study

This study will be conducted in accordance with the protocol, the current version of the Declaration of Helsinki, Good Pharmacoepidemiology Practices (GPP), ISPE GPP guideline and any local regulations. Special attention will be paid to data protection as described in Directive 95/46/EC.

Takeda will ensure that the protocol, any amendments and the Patient Information Sheet/Informed Consent Form are submitted to the relevant Independent Ethics Committees (IECs) according to local requirements.

Takeda as the sponsor is responsible for meeting the ICH requirement for yearly updates to the IECs, if applicable.

# 6.2 Independent Ethics Committee

According to all relevant local regulations, the Sponsor will:

 notify or obtain approval from the relevant IEC of the protocol, any amendments and the Patient Information Sheet / Informed Consent Form

The Sponsor will submit required documents to the IEC, such as:

- notification of substantial changes of the study documents
- notification of the end-of-study
- a summary of the study results

Sponsor/CRO will keep an updated list of all submission and approval dates of all documents submitted to the IEC and will provide the Site Responsible with a copy of this list. Copies of the documents will be distributed upon request.

# **Authorities**

Sponsor will send required documents to the competent authority (CA) and/or other national or regional authorities. Sponsor will keep an updated list of submission and approval dates and a copy of all documents submitted.

#### 6.3 Patient Information and Written Informed Consent

The Site Study Responsible must give the patient (and if applicable, legal guardian) oral and written information about the study in a form that the patient (legal guardian) can understand, and obtain the patient's (and if applicable, the patient's assent and the legal guardian's)

written consent before collection of identifiable patient information (hereinafter referred to as personal data). Before consenting, the patient (and if applicable, legal guardian) must be left with ample time to consider and to pose questions.

Since the study is observational the consent only concerns the data collection per se and is no consent to any experimental procedure or treatment.

As patients will only be eligible for study participation in case pre-rolled TachoSil® has been applied during surgery, information regarding the study will be provided to potential participants before the surgery, but consent will be collected only after the surgery.

The patient must agree that sponsor personnel, their representatives or IEC or CA personnel (national or other) may require direct access to the patient's data / personal records which were collected, processed and stored in an anonymized form.

The patient must agree that his / her data will be processed and stored in an anonymized form for evaluation of this study and any later overviews. Data may also be transferred in anonymized form to third parties, e.g. other companies or authorities, that may be located in other countries with potentially different regulations for data.

The patient and legal guardian, if applicable, has the right to withdraw his/her consent at any time without prejudice. In the Informed Consent Form it is stated that if consent is withdrawn, any data collected before withdrawal of consent will be kept unless its deletion is actively requested by the patient. The original, signed Informed Consent Forms must be kept on the Site.

For details, see the Patient Information Sheet and Informed Consent Form.

